3 STUDY DESIGN

This is a two-cohort, open-label, single site phase II study. There will be no dose escalation or expansion cohort. A total of 30 subjects will be recruited for this study; 25 in Cohort A and 5 in Cohort B.

- Cohort A: Patients who are treatment naïve to anti- PD-1 agents in the metastatic setting (prior adjuvant anti-PD1 allowed. See inclusion and exclusion criteria).
- Cohort B: Patients who previously progressed on PD-1 inhibitors.

All subjects will be treated with the same dose for both ipilimumab and pembrolizumab. The induction period consists of: intravenous pembrolizumab 200 mg plus intravenous ipilimumab 1 mg/kg every 3 weeks for up to four doses, followed by a maintenance period: intravenous pembrolizumab 200 mg every 3 weeks (as tolerated) for up to 2 years or disease progression, intolerable toxicity, withdrawal of consent, death or investigator decision.

The use of SRT (single episode) for disease progression of ≤ 5 brain lesions is permitted in this study

Low-Dose Ipilimumab with Pembrolizumab – University of Texas MD Anderson Cancer Center

2018-0875, Version 1.6

Proprietary Information of MD Anderson

per protocol-defined guidelines. Any subject who receives SRT while on study will be observed for a protocol-defined period before treatment with the study drug(s) can be resumed. The length of the observation period is determined by when in the course of treatment the subject receives SRT - during induction (pembrolizumab plus ipilimumab) or during maintenance treatment (pembrolizumab q3 weeks). Any subject who meets criteria for discontinuation following SRT will proceed to follow-up. All subjects who are discontinued from treatment will continue to be followed for safety, progression, and OS after discontinuation of study medication.

Table 1: Study Drugs and Administration Details

Study Drug	Dose
Ipilimumab	1 mg/kg every 3 weeks for up to four doses
	No Additional Ipilimumab for Study Treatment
Pembrolizumab	200mg in combination with ipilimumab, every 3 weeks, up to four doses, followed by
	Administer 200mg as a single agent every 3 weeks up to 35 doses or until disease progression or unacceptable toxicity, withdrawal of consent, or investigator decision.

Proprietary Information of MD Anderson

Subjects will undergo first CNS imaging evaluation at week 6 (\pm 3 days). Subsequently, subjects will be evaluated every 6 weeks (42 days \pm 3 days), independently of any treatment delays, with radiographic imaging to assess response to treatment, until week 30/Cycle 10. Subjects will then undergo imaging evaluation every 12 weeks (84 \pm 7 days). RECIST 1.1 will be used as the primary response rate efficacy endpoint. RECIST 1.1 will be adapted as described in Section 4. to adjust for the tumor response patterns seen with pembrolizumab treatment (e.g., tumor flare), and this adapted/modified RECIST 1.1 will be used by the sites for treatment decisions. The primary response rate efficacy endpoint will be based on independent central review using RECIST 1.1 [1]. Modified RECIST 1.1 will also be used by the local site to determine eligibility and make treatment decisions. MRI of the brain will be the primary radiological method of disease assessment using the RANO-BM criteria.

Subjects may submit an optional tumor tissue sample, if feasible, for biomarker analyses and PDL1 expression evaluation. Subjects with an inadequate archival sample may obtain a new biopsy and subjects with an inadequate newly obtained biopsy may undergo re-biopsy at the discretion of the investigator.

AEs will be monitored throughout the trial and graded in severity according to the guidelines outlined in the National Cancer Institute (NCI) Common Terminology Criteria for AEs (CTCAE) Version 4.03.

Treatment will continue as outlined in Table 1 until documented disease progression, unacceptable AEs, intercurrent illness that prevents further administration of treatment, investigator's decision to withdraw the subject, subject withdraws consent, pregnancy of the subject, noncompliance with trial treatment or procedure requirements, completion of 24 months of treatment with pembrolizumab, or administrative reasons.

Subjects who attain an investigator-determined confirmed CR may consider stopping trial treatment after receiving up to 4 doses of ipilimumab and at least 24 weeks of pembrolizumab. In addition, if a confirmed CR per modified RECIST 1.1 is attained, at least two additional treatments of pembrolizumab must be received prior to treatment discontinuation. Subjects who stop pembrolizumab with SD or better per modified RECIST 1.1 may be eligible for retreatment with a maximum of 17 doses of pembrolizumab and 4 doses of ipilimumab if they progress after stopping pembrolizumab at the discretion of the investigator according to the criteria in section 7.1.5.2.1; this retreatment will be the second course phase. Response or progression in the second course phase will not count towards the CBR or PFS endpoints in this trial. The decision to retreat will be at the discretion of the investigator only if no cancer treatment was administered since the last dose of pembrolizumab, the subject still meets the safety parameters listed in the inclusion/exclusion criteria and the trial remains open (refer to section 7.1.5.2.1 for further details).

After the end of protocol treatment, each subject will be followed for 30 days for AE monitoring. (SAEs will be collected for 90 days after the end of treatment). Subjects who discontinue treatment for reasons other than disease progression will have survival follow-up (SFU) for disease status until disease progression, initiating a non-study cancer treatment, withdrawing consent, or becoming lost to follow-up. All subjects will be followed by telephone contact for OS until death, withdrawal of consent or the end of the trial, whichever comes first

Proprietary Information of MD Anderson

4. MATERIALS AND METHODS

4.1 SUBJECTS

4.1.1 Inclusion Criteria

1. Age \geq 18 years old.
2. Life Expectancy $>$ 12 weeks
3. Subjects must have signed and dated an IRB/IEC approved written informed consent form in accordance with regulatory and institutional guidelines. This must be obtained before the performance of any protocol related procedures that are not part of normal subject care.

Subjects must be willing and able to comply with scheduled visits, treatment schedule, laboratory testing, and other requirements of the study.
4. Histologically confirmed malignant melanoma with measurable metastases in the brain (\geq 0.5 cm)
5. At least one measurable intracranial target lesion, which previously was not treated with local therapy (no prior SRS to this lesion).
 - Largest diameter of \geq 0.5cm, but \leq 3cm as determined by contrast-enhanced MRI
6. Representative formalin-fixed paraffin-embedded (FFPE) tumor specimens in paraffin blocks (blocks are preferred) **OR** at least 4 unstained slides, with an associated pathology report, for testing of tumor PD-L1 expression:
 - Tumor tissue should be of good quality based on total and viable tumor content.
 - Patients who do not have tissue specimens may undergo a biopsy during the screening period. Acceptable samples include core-needle biopsies for deep tumor tissue or excisional, incisional, punch, or forceps biopsies for cutaneous, subcutaneous, or mucosal lesions.
 - Tumor tissue from bone metastases is not evaluable for PD-L1 expression and is therefore not acceptable.
 - However, if repeat biopsy is not feasible, and no archival tissue available patient still may be enrolled.
7. Prior SRT and prior excision of up to 5 MBM is permitted if there has been complete recovery, with no neurologic sequelae, and measurable lesions remain. Growth or change in a lesion previously irradiated will not be considered measurable. Regrowth in cavity of previously excised lesion will not be considered measurable.
 - Any prior SRT to brain lesions or prior excision must have occurred \geq 1 weeks before the start of dosing for this study.
8. Radiation to NON-CNS lesions. Prior radiation to NON-CNS is allowed, and does not require a washout period for treatment initiation.

Proprietary Information of MD Anderson

9. Subjects must be free of neurologic signs and symptoms related to metastatic brain lesions and must not have required or received systemic corticosteroid therapy in the 10 days prior to beginning protocol therapy.

10. ECOG performance status ≤ 1 .

11. Adequate organ function as described below.

System	Laboratory Value
Hematological	
Absolute neutrophil count (ANC)	$\geq 1500/\mu\text{L}$
Platelets	$\geq 100\,000/\mu\text{L}$
Hemoglobin	$\geq 9.0\text{ g/dL}$ or $\geq 5.6\text{ mmol/L}^a$
Renal	
Creatinine OR Measured or calculated ^b creatinine clearance (GFR can also be used in place of creatinine or CrCl)	$\leq 1.5 \times \text{ULN OR}$ $\geq 30\text{ mL/min}$ for participant with creatinine levels $>1.5 \times$ institutional ULN
Hepatic	
Total bilirubin	$\leq 1.5 \times \text{ULN OR}$ direct bilirubin $\leq \text{ULN}$ for participants with total bilirubin levels $>1.5 \times \text{ULN}$
AST (SGOT) and ALT (SGPT)	$\leq 2.5 \times \text{ULN}$ ($\leq 5 \times \text{ULN}$ for participants with liver metastases)
Coagulation	
International normalized ratio (INR) OR prothrombin time (PT) Activated partial thromboplastin time (aPTT)	$\leq 1.5 \times \text{ULN}$ unless participant is receiving anticoagulant therapy as long as PT or aPTT is within therapeutic range of intended use of anticoagulants
ALT (SGPT)=alanine aminotransferase (serum glutamic pyruvic transaminase); AST (SGOT)=aspartate aminotransferase (serum glutamic oxaloacetic transaminase); GFR=glomerular filtration rate; ULN=upper limit of normal.	
^a Criteria must be met without erythropoietin dependency and without packed red blood cell (pRBC) transfusion within last 2 weeks.	
^b Creatinine clearance (CrCl) should be calculated per institutional standard.	
Note: This table includes eligibility-defining laboratory value requirements for treatment; laboratory value requirements should be adapted according to local regulations and guidelines for the administration of specific chemotherapies.	

12. Women of child-bearing potential (WOCBP) must not be breastfeeding and must have a negative pregnancy test within 3 days prior to initiation of dosing. She must agree to use an acceptable method of birth control from the time of the negative pregnancy test up to 120 days after the last dose of study drug. WOCBP must agree to adhere to the contraceptive guidance in Appendix 5. **Note:** A female participant is eligible to participate if she is not a woman of childbearing potential as defined in Appendix 5.

Proprietary Information of MD Anderson

13. Fertile men must agree to use an acceptable method of birth control as described in Appendix 5 while on study drug and up to 120 days after the last dose of study drug and also refrain from donating sperm during this period.
14. All associated toxicity from previous or concurrent cancer therapy must be resolved (to ≤ grade 1 or baseline) prior to study treatment administration. This excludes non-serious toxicities.
15. Steroids for physiological replacement are allowed.

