 - a. **Note:** Without known history, testing needs to be performed to determine eligibility. Hepatitis C antibody (Ab) testing is allowed for screening purposes in countries where HCV RNA is not part of standard of care.

Proprietary Information of MD Anderson

10. Has a known history of human immunodeficiency virus (HIV) infection. No HIV testing is required unless mandated by local health authority.
11. The use of corticosteroids is not allowed for 10 days prior to initiation of therapy (based upon 5 times the expected half-life of dexamethasone) except patients who are taking steroids for physiological replacement. If alternative corticosteroid therapy has been used, consultation with the PI is required to determine the washout period prior to initiating study treatment.
12. Subjects with a condition requiring systemic treatment with either corticosteroids (> 10 mg daily prednisone equivalent) or other immunosuppressive medications within 14 days of study initiation. Inhaled or topical steroids, and adrenal replacement steroid doses > 10 mg daily prednisone equivalent, are permitted in the absence of active autoimmune disease.
13. Subjects with history of life-threatening toxicity related to prior ipilimumab adjuvant therapy except those that are unlikely to re-occur with standard countermeasures (e.g. hormone replacement after adrenal crisis)
14. Major surgical procedure, open biopsy (excluding skin cancer resection), or significant traumatic injury within 14 days of initiating study drug (unless the wound has healed) or anticipation of the need for major surgery during the study.
15. Non-healing wound, ulcer, or bone fracture.
16. Women who are breast-feeding or pregnant.
17. Uncontrolled intercurrent illness (i.e., active infection \geq grade 2) or concurrent condition that, in the opinion of the Investigator, would interfere with the study endpoints or the subject's ability to participate.
18. History of clinically significant cardiac disease or congestive heart failure $>$ New York Heart Association (NYHA) class 2. Subjects must not have unstable angina (anginal symptoms at rest) or new-onset angina within the last 3 months or myocardial infarction within the past 6 months.
19. Investigational drug use within 14 days (or 5 half-lives, whichever is longer) of the first dose of ipilimumab and pembrolizumab.
20. Has a history of non-infectious pneumonitis that required steroids or current pneumonitis.

4.2

TRIAL TREATMENTS

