4.2.2.1 Pembrolizumab Dose Modifications

See the table below for Dose Modification guidelines for pembrolizumab.

Table 3: Dose modification and toxicity management guidelines for immune-related AEs associated with pembrolizumab monotherapy and IO Combinations

General instructions:
 
 1. Severe and life-threatening irAEs should be treated with IV corticosteroids followed by oral steroids. Other immunosuppressive treatment should begin if the irAEs are not controlled by corticosteroids. 2. Study intervention must be permanently discontinued if the irAE does not resolve or the corticosteroid dose is not \leq10 mg/day within 12 weeks of the last study intervention treatment. 3. The corticosteroid taper should begin when the irAE is \leq Grade 1 and continue at least 4 weeks. 4. If study intervention has been withheld, study intervention may resume after the irAE decreased to \leq Grade 1 after corticosteroid taper. 				
--	--	--	--	--

irAEs	Toxicity Grade (CTCAE v5.0)	Action With Pembrolizumab	Corticosteroid and/or Other Therapies	Monitoring and Follow-up
Pneumonitis	Grade 2	Withhold	
 • Administer corticosteroids (initial dose of 1 to 2 mg/kg prednisone or equivalent) followed by taper 	
 • Monitor participants for signs and symptoms of pneumonitis
	Recurrent Grade 2, Grade 3 or 4	Permanently discontinue	
 • Add prophylactic antibiotics for opportunistic infections 	
 • Evaluate participants with suspected pneumonitis with radiographic imaging and initiate corticosteroid treatment
Diarrhea/Colitis	Grade 2 or 3	Withhold	
 • Administer corticosteroids (initial dose of 1 to 2 mg/kg prednisone or equivalent) followed by taper 	
 • Monitor participants for signs and symptoms of enterocolitis (ie, diarrhea, abdominal pain, blood or mucus in stool with or without fever) and of bowel perforation (ie, peritoneal signs and ileus)
	Recurrent Grade 3 or Grade 4	Permanently discontinue		
 • Participants with \geqGrade 2 diarrhea suspecting colitis should consider GI consultation and performing endoscopy to rule out colitis

irAEs	Toxicity Grade (CTCAE v5.0)	Action With Pembrolizumab	Corticosteroid and/or Other Therapies	Monitoring and Follow-up

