Nephritis: grading according to increased creatinine or acute kidney injury	Grade 2	Withhold	
 Administer corticosteroids (prednisone 1 to 2 mg/kg or equivalent) followed by taper 	
 Monitor changes of renal function
	Grade 3 or 4	Permanently discontinue		
Neurological Toxicities	Grade 2	Withhold	
 Based on severity of AE administer corticosteroids 	
 Ensure adequate evaluation to confirm etiology and/or exclude other causes
	Grade 3 or 4	Permanently discontinue		
Myocarditis	Grade 1	Withhold	
 Based on severity of AE administer corticosteroids 	
 Ensure adequate evaluation to confirm etiology and/or exclude other causes
	Grade 2, 3 or 4	Permanently discontinue		
Exfoliative Dermatologic Conditions	Suspected SJS, TEN, or DRESS	Withhold	
 Based on severity of AE administer corticosteroids 	
 Ensure adequate evaluation to confirm etiology or exclude other causes
	Confirmed SJS, TEN, or DRESS	Permanently discontinue		
All Other irAEs	Persistent Grade 2	Withhold	
 Based on severity of AE administer corticosteroids 	
 Ensure adequate evaluation to confirm etiology or exclude other causes
	Grade 3	Withhold or discontinue based on the event ^e		
	Recurrent Grade 3 or Grade 4	Permanently discontinue		

^aAE(s)=adverse event(s); ALT= alanine aminotransferase; AST=aspartate aminotransferase; CTCAE=Common Terminology Criteria for Adverse Events; DRESS=Drug Rash with Eosinophilia and Systemic Symptom; GI=gastrointestinal; IO=immuno-oncology; ir=immune related; IV=intravenous; SJS=Stevens-Johnson Syndrome; T1DM=type 1 diabetes mellitus; TEN=Toxic Epidermal Necrolysis; ULN=upper limit of normal.

Note: Non-irAE will be managed as appropriate, following clinical practice recommendations.

irAEs	Toxicity Grade (CTCAE v5.0)	Action With Pembrolizumab	Corticosteroid and/or Other Therapies	Monitoring and Follow-up
^a				
^a			AST/ALT: >3.0 to 5.0 x ULN if baseline normal; >3.0 to 5.0 x baseline, if baseline abnormal; bilirubin: >1.5 to 3.0 x ULN if baseline normal; >1.5 to 3.0 x baseline if baseline abnormal	
^b				

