7.1 ADVERSE EVENT ASSESSMENT AND REPORTING

An adverse event is defined as any untoward medical occurrence in a patient or clinical investigation subject administered a pharmaceutical product and which does not necessarily have to have a causal relationship with this treatment. An adverse event can therefore be any unfavorable and unintended sign (including an abnormal laboratory finding, for example), symptom, or disease temporally associated with the use of a medicinal product or protocol - specified procedure, whether or not considered related to the medicinal product or protocol specified procedure. Any worsening (i.e., any clinically significant adverse change in frequency and/or intensity) of a preexisting condition that is temporally associated with the use of the investigational products is also an adverse event.

Changes resulting from normal growth and development that do not vary significantly in frequency or severity from expected levels are not to be considered adverse events. Examples of this may include, but are not limited to, teething, typical crying in infants and children and onset of menses or menopause occurring at a physiologically appropriate time.

Adverse events may occur during clinical trials or as prescribed in clinical practice, from overdose (whether accidental or intentional), from abuse and from withdrawal.

Progression of the cancer under study is not considered an adverse event.

From the time of initial protocol treatment through 30 days following cessation of treatment, all adverse events must be recorded. Such events will be recorded at each examination in the medical record. The reporting timeframe for adverse events meeting any serious criteria is described in Section 7.1.1. The investigator will make every attempt to follow all subjects with non-serious adverse events for outcome.

An investigator who is a qualified physician will evaluate all adverse events according to the NCI Common Terminology for Adverse Events (CTCAE), version 4.03. Any adverse event which changes CTCAE grade over the course of a given episode will have each change of grade recorded on the adverse event case report forms/worksheets.

All adverse events regardless of CTCAE grade must also be evaluated for seriousness.

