For studies in which multiple agents are administered as part of a combination regimen, the investigator may attribute each adverse event causality to the combination regimen or to a single agent of the combination. In general, causality attribution should be assigned to the combination regimen (i.e., to all agents in the regimen). However, causality attribution may be assigned to a single agent if in the investigator's opinion; there is sufficient data to support full attribution of the adverse experience to the single agent.

All Adverse Events will be reported to regulatory authorities, IRB/IECs and investigators in accordance with all applicable global laws and regulations.

Table 9: Evaluating Adverse Events

V4.03 CTCAE Grading	Grade 1	Mild; asymptomatic or mild symptoms; clinical or diagnostic observations only; intervention not indicated.
	Grade 2	Moderate; minimal, local or noninvasive intervention indicated; limiting age-appropriate instrumental ADL.
	Grade 3	Severe or medically significant but not immediately life-threatening; hospitalization or prolongation of hospitalization indicated; disabling; limiting self-care ADL.
	Grade 4	Life threatening consequences; urgent intervention indicated.
	Grade 5	Death related to AE

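### Inclusion 14 exempts all non-serious prior toxicity with no grade cap, so some unresolved Grade 2 immune events that Table 3 would hold drug for do not bar dose 1

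*Combined protocol and SAP*

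**What the plan says.** Section 4.1.1, inclusion 14, sets a grade 1 or baseline rule for toxicity from previous or concurrent cancer therapy and qualifies it in one sentence: "This excludes non-serious toxicities". Nothing says which toxicities are meant or up to what grade.

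Section 7.1 treats seriousness as a separate judgement: "All adverse events regardless of CTCAE grade must also be evaluated for seriousness". Table 9 defines Grade 2 as "Moderate; minimal, local or noninvasive intervention indicated; limiting age-appropriate instrumental ADL".

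Table 3 (section 4.2.2.1) withholds pembrolizumab for Grade 2 neurological toxicity and for persistent Grade 2 events in its row for all other immune-related events. For both rows the steroid column reads "Based on severity of AE administer corticosteroids". General instruction 4 states "If study intervention has been withheld, study intervention may resume after the irAE decreased to" grade 1 or lower. The text after the table holds both drugs when an event is immune-related.

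Two other entry criteria bear directly on the point. Inclusion 9 says "Subjects must be free of neurologic signs and symptoms related to metastatic brain lesions" and that they "must not have required or received systemic corticosteroid therapy in the 10 days prior to beginning protocol therapy". Exclusion 12 bars, within 14 days of study initiation, "Subjects with a condition requiring systemic treatment with either corticosteroids" above 10 mg daily prednisone equivalent or other immunosuppressants.

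**The concern.** Inclusion 14 exists to stop patients starting treatment with unresolved toxicity above grade 1. The first grade it should stop is Grade 2, and Grade 2 events can be non-serious. Read with the protocol's own meaning of serious, the exemption can cancel the rule exactly where it should act.

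What is at stake is patient safety at the first dose. That dose gives ipilimumab and anti-PD-1 together, and section 4.2.2 warns that the combination may worsen shared and other toxicities. Cohort B consists of patients who progressed on PD-1 inhibitors, with a minimum washout of 3 weeks (exclusion 5), so leftover immune toxicity at entry is plausible. A patient could be started in a state in which the protocol would not re-dose someone already on study.

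**Working it through.** The plan gives no figure to reproduce. The check sets the criteria side by side.

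**Step 1. Can a Grade 2 event be non-serious?** The criteria in Table 9 and section 7.1.1 include death, threat to life, lasting disability, hospitalisation, congenital anomaly and other important medical events. None is part of the Grade 2 definition. The important-medical-event criterion can make a Grade 2 event serious, but only through medical judgement. So a Grade 2 event can be non-serious, and inclusion 14 then exempts it.

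**Step 2. For which Grade 2 events does Table 3 stop drug?** Table 3 has 12 event rows.

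- Withhold: pneumonitis, colitis, hepatic, hypophysitis, nephritis, neurological, other persistent Grade 2 = 7.
- Permanent stop: myocarditis = 1.
- Continue: hyperthyroidism, hypothyroidism = 2.
- Action not set by Grade 2: diabetes/hyperglycaemia, exfoliative skin conditions = 2.

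Rows with drug stopped at Grade 2: 7 + 1 = 8. Check: 8 + 2 + 2 = 12.

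**Step 3. Which of the 8 do other criteria close?** Table 3 and section 4.5 direct steroids at Grade 2 for 5 rows: pneumonitis, colitis, hepatic, hypophysitis and nephritis. On a natural reading these patients have required systemic steroids, so inclusion 9 and exclusion 12 bar them. Hypophysitis controlled on physiological replacement is tolerated under inclusion 15. That leaves 8 − 5 = 3 rows in which steroids depend on severity. Exclusion 18 (clinically significant cardiac disease) largely closes myocarditis: 3 − 1 = 2 rows open, namely neurological toxicity and other persistent Grade 2 events.

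**Step 4. Does any remaining criterion close these two?**

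| Criterion | Why it does not settle them |
|---|---|
| Inclusion 7 | Neurologic sequelae of prior SRT or excision only |
| Inclusion 9, symptom clause | Signs from brain lesions only, not drug neurotoxicity |
| Inclusion 10 (ECOG 0–1) | Removes some symptomatic patients; not a toxicity limit |
| Exclusion 6 | Silent on whether a drug-induced event is autoimmune disease; admits conditions that need an external trigger to recur |
| Exclusion 7 | Tests ability to comply, as judged |
| Exclusion 13 | Life-threatening toxicity of adjuvant ipilimumab only |
| Exclusion 17 | For a concurrent condition, investigator opinion with no toxicity grade |
| Baseline NANO (4.4.11) | Records neurologic function; sets no entry threshold |

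None is a mandatory bar on a non-serious, unresolved Grade 2 event of either kind managed without systemic steroids.

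**Step 5. How sensitive is this to the reading of the steroid criteria?** If inclusion 9 and exclusion 12 are applied only when steroids were actually taken, colitis and nephritis reopen: 2 + 2 = 4 rows. Hepatic events reopen in part as well, because inclusion 11 allows AST/ALT up to 5 × ULN with liver metastases, while Table 3's Grade 2 band is above 3 to 5 × ULN from a normal baseline. So 4 is not a ceiling on that reading.

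**Step 6. Who could be exposed?** Mainly Cohort B: 5 of 30 patients, 5/30 = 17%. Cohort A may include prior adjuvant anti-PD-1 or adjuvant or neoadjuvant ipilimumab. Exclusion 5, however, bars progression within six months of the last dose of adjuvant anti-PD-1 and sets a 6-month ipilimumab washout, so recent toxicity is less likely there. The documents give no count of patients with unresolved toxicity.

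**The case against.** The strongest objection is that the two rules have different purposes. Table 3 manages events once study drug is being given, and instruction 4 speaks of study intervention that has been withheld. If Table 3 does not reach dose 1, nothing in the protocol is contradicted; if it does, drug would be withheld and the gap closes. This stands against a reading that a reader might be tempted to take, that the protocol contradicts itself. It does not remove the mismatch: entry is looser than re-dosing for the same event.

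Second, judgement gives real protection. An investigator can class a worrying Grade 2 neurological event as an important medical event, treat an unresolved immune event as active autoimmune disease under exclusion 6, or use exclusion 7 or 17. Exclusion 6's allowance fits quiescent conditions better than an unresolved event. ECOG 0–1 and the baseline neurologic examination narrow the group further. All of this makes the gap smaller, but none of it is a rule.

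Third, the authors may have meant only clinically trivial toxicities such as alopecia. That is likely, but the text does not say so, and non-serious has a wider meaning in this protocol.

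Fourth, a tighter rule could delay or exclude patients with a poor outlook; section 1.1.1 gives a median survival of 4 months after diagnosis of brain metastasis. That is a fair cost, and it is the reason to keep the baseline alternative.

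**Conclusion.** The point holds in a limited form. As written, a patient with a non-serious, unresolved Grade 2 drug-related neurological event, or another persistent Grade 2 immune event managed without systemic steroids, can meet every mandatory entry criterion and receive the first combination dose, although Table 3 would withhold drug for that event on study.

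The conclusion rests on two readings: that non-serious carries its section 7.1 meaning, and that the steroid criteria bar events for which the protocol directs steroids.

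Three stronger inferences are not supported:

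- That any Grade 2 immune event can enter. On the natural reading, 5 of the 8 relevant rows are barred by the steroid criteria (apart from hypophysitis on replacement), and myocarditis is largely barred by exclusion 18.
- That 2 of 8 rows measures risk. It counts table rows, one of which is a catch-all, and says nothing about how often such patients present.
- That the clinical benefit rate is affected. Nothing in the documents shows this.

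The number of patients concerned is unknown and probably small, with most relevance to the 5 in Cohort B. This is a cheap safety improvement, not a flaw in the trial's inference.

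**What to change.** In inclusion 14, replace the exempting sentence with a named exemption in line with exclusion 6 and inclusion 15: alopecia, vitiligo or other skin disorders that need no systemic treatment, and endocrinopathy controlled on stable hormone replacement. Require all other immune-related toxicity from prior therapy to be grade 1 or less, or back to the patient's baseline before that therapy, before dose 1. Leave the inclusion 11 laboratory limits unchanged. The sponsor's clinicians should settle the final list.

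The cost is a short change to one criterion in an amendment. A few candidates will wait for resolution. A few with stable, permanent Grade 2 sequelae of prior therapy may be excluded, because their baseline before that therapy was better; if the clinicians consider such patients safe to treat, those sequelae should be added to the list by name.
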